5.7. Subject Follow-up after Withdrawal

Upon withdrawal from the study, no further study data will be collected or study visits will occur for the subject.

5.8. Medications

There are no medications that are required for this study. All cardiovascular medications will be collected.

6. STUDY DEVIATIONS

A study deviation is defined as an event within a study that did not occur according to the Clinical Investigation Plan or the Clinical Trial Agreement.

Prior approval by the Medtronic study manager is expected in situations where the investigator anticipates, contemplates, or makes a conscious decision to deviate. Prior approval is not required when a deviation is necessary to protect the life or physical wellbeing of a subject in an emergency or in unforeseen situations beyond the investigator's control (e.g. subject failure to attend scheduled follow-up visits, inadvertent loss of data due to computer malfunction, inability to perform required procedures due to subject illness, etc.).

For medically justifiable conditions which preempt a subject's ability to complete a study-required procedure, it may be permitted to complete only one deviation Case Report Form which will apply to all visits going forward. This may also apply for other unforeseen situations (e.g. the subject permanently refuses to complete a study required procedure and the data will not contribute to the primary end point analysis, etc.). However, prior approval from Medtronic is required for such situations.

All study deviations must be reported on the Case Report Form regardless of whether medically justifiable, pre-approved by Medtronic, an inadvertent occurrence, or taken to protect the subject in an emergency. The deviation must be recorded with an explanation for the deviation and corrective/ preventative action(s).

In the event the deviation involves a failure to obtain a subject's consent, or is made to protect the life or physical wellbeing of a subject in an emergency, the deviation must be reported to the MEC/IRB (where applicable) as well as Medtronic within five (5) working days. Reporting of all other study deviations should comply with MEC/IRB policies and/or local laws and must be reported to Medtronic as soon as possible upon the center becoming aware of the deviation. Reporting of deviations must comply with IRB/MEC policies, local laws, and or regulatory agency requirements.

Medtronic is responsible for analyzing deviations, assessing their significance, and identifying any additional corrective and/or preventive actions (e.g. amend the Clinical Investigation Plan, conduct additional training, terminate the investigation, etc.). Repetitive or serious investigator compliance issues may represent a need to initiate a corrective action plan with the investigator and site, and in some cases, necessitate freezing enrollment until the problem is resolved or ultimately terminating the investigator's participation in the study. Medtronic will provide center-specific reports to investigators summarizing information on deviations that occurred at the investigational site on a periodic basis.

7. ADVERSE EVENTS

The collection of adverse event data is not required to meet the objective(s) of this clinical trial. The products used in the clinical trial are market approved and used within the current indications for use as indicated in the product labeling. However, it is the responsibility of the Investigator to abide by any adverse event reporting requirements stipulated by local laws and regulations and the site's Investigational Review Board (IRB) or Medical Ethics Committee (MEC). User (Investigator) reporting of events to regulatory authorities related to market approved products may be required.

7.1. Vigilance Reporting

It is the responsibility of the investigator to report all product complaints and malfunctions immediately via the regular channels for CE marked products. The reporting of product complaints and malfunctions of these CE-labeled devices is not part of the clinical study and should be done by the investigator.

8. SUBJECT DEATH

8.1. Data Collection

Subject deaths will be documented on the Study Exit form. The date of death and classification of cardiovascular relatedness, if known, will also be documented. It is the responsibility of the Investigator to abide by any death reporting requirements stipulated by local laws and regulations and the site's Medical Ethics Committee (MEC).

User (Investigator) reporting of deaths to regulatory authorities related to market approved products may be required.

9. RISK ANALYSIS

All implantable systems (pacemaker and lead(s)) utilized in this study are market released and are used according to medical, technical and ethical standards without any change to the approved use of the system. The safety and clinical performance of the market released systems have been demonstrated through previous pre-clinical testing and clinical studies in similar populations, but not necessarily the same population as this study. The risks are described in the informed consent.

9.1. Potential Benefits

There are no direct benefits to the patient for participating in IMPROVE Brady. However, information gained from the study will contribute to the body of knowledge regarding diagnosis and treatment of patients with SND and may help improve the quality of care for these patients.

10. PLANNED STUDY CLOSURE, EARLY TERMINATION OF STUDY OR STUDY SUSPENSION

10.1. Planned Study Closure

Study Closure is a process initiated by distribution of an initial study closure letter. Study closure is defined as closure of a clinical study that occurs when Medtronic and/or regulatory requirements have been satisfied per the Clinical Investigation Plan and/or by a decision by Medtronic or regulatory authority, whichever occurs first. The study closure process is complete upon distribution of the Final Report or after final payments, whichever occurs last. IRB/MEC re-approvals are required until the overall study closure process is complete.

10.2. Early Termination OR Suspension

Early Termination of the Study is the closure of a clinical study that occurs prior to meeting defined endpoints. This is possible for the whole study, or a single center. Study Suspension is a temporary postponement of study activities related to enrollment. This is possible for the whole study or a single center.

Criteria

Study Termination or Suspension

Possible reasons for considering study suspension or early termination of the study may include:

- None of the study subjects have been implanted with an indicated IPG at the completion of Phase I
- Enrollment is slower than anticipated

Investigator/Center Termination or Suspension

Possible reasons for clinical investigator or center termination or suspension include but are not limited to:

- Failure to obtain initial MEC/Head of Medical Institution approval or annual renewal of the study (where applicable)
- Consistent non-compliance to the clinical investigation (e.g. failure to adhere to inclusion/exclusion criteria, failure to follow subjects per scheduled follow-ups, etc.)
- Lack of enrollment
- Noncompliance to regulations and the terms of the Clinical Trial Agreement (e.g. failure to submit data in a timely manner, failure to follow-up on data queries and monitoring findings in a timely manner, etc.)
- MEC suspension of the center
- Fraud or fraudulent misconduct is discovered (as defined by local law and regulations)
- Investigator request (e.g. no longer able to support the study)

Procedures

If Medtronic terminates or prematurely suspends the study:

Medtronic will promptly inform the clinical investigators of the termination or suspension and the reasons and inform the regulatory authority (ies) (where required per regulatory requirements). In the case of study termination or suspension for reasons other than a temporary MEC approval lapse, the investigator will promptly inform the MEC.

- In the case of study termination, the investigator must inform the subjects and may inform the personal physician of the subjects to ensure appropriate care and follow-up is provided.
- In the case of a study suspension, subjects already enrolled should continue to be followed out of consideration of their safety, rights and welfare.

If the investigator terminates or suspends the study without prior agreement of Medtronic:

- The investigator will promptly inform Medtronic and provide a detailed written explanation of the termination or suspension.
- The investigator will promptly inform the institution (where required per regulatory requirements).
- The investigator will promptly inform the MEC (where applicable).

If the MEC terminates or suspends its approval of the study:

- The investigator will promptly inform Medtronic and provide a detailed written explanation of the termination or suspension within 5 business days.
- Subject enrollment must stop until the MEC suspension is lifted.
- Subjects already enrolled should continue to be followed in accordance with IRB/MEC policy or its determination that an overriding safety concern or ethical issue is involved.
- The investigator will inform his/her institution (where required per local requirements).
- The investigator will promptly inform the subjects and/or the personal physician of the subjects, with the rationale for the study termination or suspension.

11. STATISTICAL METHODS AND DATA ANALYSIS

Medtronic statisticians or designees will conduct all statistical analysis. The sample size package PASS 2008 was used for sample size evaluation. In this study, it is hypothesized that the use of a practice-specific process improvement intervention consisting of education, diagnostic algorithm(s) and documentation tools that advocate and reinforce adherence to consensus treatment guidelines will improve the quality of care for patients with sinus node dysfunction (SND). The two primary endpoints are the impact of the intervention on the diagnosis of subjects with SND and whether SND indicated subjects receive a referral for an IPG therapy. In current practice, both of these proportions are unknown but have been estimated for a set of patients meeting the study inclusion criteria. The sample size calculations will use exact confidence intervals and tests to compare rates and binomial proportions.

11.1. Primary Objective(s)

Primary Objective #1

Evaluate the impact of the intervention on the diagnosis of SND.

Hypothesis

The primary objective will be tested with the following hypothesis:

$$H_0: p_{1t} = p_{2t}$$

$$H_A: p_{1t} \neq p_{2t}$$

where p_{1t} is the proportion of patients with SND in Phase I and p_{2t} is the proportion of patients with SND in Phase II at time point t .

Endpoint Definition

The absolute change in the proportion of subjects diagnosed with SND at pre-specified time points ($\% = \text{number diagnosed} / \text{number enrolled} \times 100$ at time point $t = 6$, or t is a multiple of 6 representing any additional 6-month interval for which there is sufficient follow-up information) and the absolute change in the number of subjects diagnosed with SND per person-year.

Analysis Methods

A. Statistical Methodology

To compare the proportion of subjects with an SND diagnosis pre-intervention (Phase I) to the proportion post-intervention (Phase II), a binomial exact test will determine statistical significance. The proportion of subjects diagnosed will be evaluated at multiple time points because the time to diagnosis is expected to vary by hospital. Thus, times are pre-specified starting at 6 months and any additional 6-month interval thereafter for which there is sufficient follow-up data available to compare study phases. Proportions calculated at all available time points will be reported. Additionally a Poisson regression will compare the average number of subjects with an SND diagnosis in Phase I and Phase II where the subject time in study is treated as an offset in the model. The above described tests will be performed separately within site as well as overall.

B. Determination of Patients/Data for Analysis

All subjects that are enrolled in the study and that meet study inclusion/exclusion criteria will be included in the determination of the proportion estimates. The proportion estimates will be calculated based on information from fixed time points at 6 months of follow-up, and any additional 6-month interval thereafter for which there is sufficient follow-up data available to compare study phases. The number of subjects that obtain a SND diagnosis by pre-specified time point t is included in the numerator and the number of subjects enrolled is included in the denominator.

Sample Size Methods and Assumptions

The proportion of SND diagnoses in subjects with bradycardia is currently unknown. The power calculations conservatively assume that the SND diagnosis will be 10% at six months of follow-up, or equivalently an SND incidence of 0.2 diagnoses per person-year. If 200 subjects are collected each in Phase I and in Phase II, assuming a type I error of 0.05 and power of 0.80, a binomial exact test will detect an increase in SND diagnosis of at least 10%. For example, the study will find a statistically significant difference between a Phase I SND percentage of 10% at 6 months and a Phase II SND percentage of 20% at 6 months. If the proportion of SND diagnoses is smaller than 10%, there will be more power to detect significant differences in the diagnosis proportion. It is expected that the study attrition rate may be 5% of the study population. To account for attrition, the sample size for Phase I will be a minimum of 210 subjects and for Phase II will be a minimum of 210 subjects.

Primary Objective #2

Evaluate the impact of the intervention on SND subjects receiving a referral for an indicated IPG device.

Hypothesis

The primary objective will be tested with the following hypothesis:

$$H_0: p_{1t} = p_{2t}$$

$$H_A: p_{1t} \neq p_{2t}$$

where p_{1t} is the proportion of patients referred for an IPG in Phase I and p_{2t} is the proportion of patients in Phase II at time point t .

Endpoint Definition

The absolute change in the proportion of subjects receiving therapy referral for an indicated IPG at pre-specified time points ($\% = \text{number receiving IPG}/\text{number with SND diagnosis} \times 100$ at time point t where $t = 3, 6$, and any additional 3-month interval for which there is sufficient follow-up information) and the absolute change in the number of subjects implanted per person-year.

Analysis Methods

Statistical Methodology

To compare the proportion of SND subjects that receive a referral for indicated therapy pre-intervention (Phase I) to the proportion post-intervention (Phase II), a binomial exact test will determine statistical significance. The proportion of subjects diagnosed will be evaluated at multiple time points because the time from diagnosis to implant is expected to vary by hospital. Shorter time intervals will be used to evaluate the proportion of referrals than for the proportion of diagnosis because implants typically occur more quickly than the SND diagnosis. Thus, times are pre specified starting at 3 months and any additional 3-month interval thereafter for which there is sufficient follow-up data available to compare study phases. Proportions calculated at all available time points will be reported. Additionally, a Poisson regression will compare the average number of subjects with an implant where the subject time in study beginning at the time of SND diagnosis is treated as an offset in the model.

Determination of Patients/Data for Analysis

The number of subjects that meet inclusion criteria and obtain an SND diagnosis shall be included in this analysis. The proportion estimates will be calculated based on information from fixed time points at 3 months of follow-up, 6 months of follow-up, and any additional 3-month interval thereafter for which there is sufficient follow-up data available to compare study phases. The number of subjects that obtain an IPG referral by pre-specified time point $t = 3, 6, \text{ etc.}$, will be included in the numerator and the number of subjects with an SND diagnosis will be included in the denominator.

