4.3. Study Design

There are two phases for Brady MX

Figure 1: IMPROVE Brady Study Design

Phase I: This phase of the study serves as a control period. During Phase I physicians will assess and treat subjects per their site’s standard care practice.

Enrollment for Phase I is anticipated to occur for approximately 6 months but will continue until a minimum of 210 subjects have been enrolled. For subjects enrolled during Phase I, collection of diagnostic assessment and implant data will be complete 6 months after the last enrollment. At that time, all Phase I subjects will be exited

Phase II:
The objective of the Brady MX study is to provide investigators with comprehensive resources that may be adapted by the Principal Investigator and his/her colleagues to create a practice specific process improvement intervention to improve the quality of care for patients.

At the completion of Phase I, the Principal Investigator and co-investigators will complete an educational workshop and be given access to the Brady MX toolkit. In addition, the Principal Investigator and his/her colleagues are encouraged to adapt tools from the Brady MX toolkit to create a practice specific process improvement intervention.

Immediately following completion of the educational workshop, study investigators will receive written authorization from Medtronic that they are authorized to enroll subjects in Phase II. Enrollment during this phase is anticipated to occur for approximately 6 months but will continue until a minimum of 210 subjects have been enrolled.

The Brady MX process improvement intervention toolkit may include an education workshop, diagnostic algorithm(s), patient video and tools for investigators to educate their patients on their disease state, available therapy options, and benefits and risks associated with the therapy options.

For subjects enrolled during Phase II collection of diagnostic assessment data will be complete 6 months after last enrollment. At that time, any subjects without a diagnosis will be exited from the study.

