4.4. Minimization of Bias

Potential sources of bias in this study may result from the Hawthorne effect, selection of study centers, selection of subjects, treatment of subjects, and evaluation of study data. The following methods have been incorporated into the study to minimize potential bias.

- Center selection criteria, documented under separate cover, will need to be met prior to participation in Brady MX. Study center characteristics will be collected at activation on possible differences that may affect the primary endpoints. Centers will be used as their own control
- Subjects will be screened to confirm eligibility with the help of screening logs, for enrollment with defined inclusion/exclusion criteria prior to enrollment
- Subject demographics will be collected at baseline on possible differences that may affect the primary endpoints
- It is anticipated that the distribution of subjects with various co-morbidities will vary by study centers. To minimize potential bias, all sites will be encouraged to enroll at least 5 subjects in each study Phase and enrollment at a site cannot exceed 42 subjects per phase to ensure a more even distribution of data
- All study Clinicians will be required to follow the Clinical Investigation Plan
- All study clinicians and Medtronic personnel will be trained on their respective aspects of the clinical investigation plan using standardized training materials.

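### The overall primary test pools patients with no site term, and the sample size allows nothing for site-by-phase variation, although the intervention is delivered and adapted by practice in at most 10 sites

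*Combined protocol and SAP*

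**What the plan says.** - **Test.** Section 11.1, Primary Objective #1: the Phase I and Phase II proportions diagnosed are compared and "a binomial exact test will determine statistical significance". The accompanying Poisson regression names only a time offset. The same tests are to be run within each site and overall.
- **Sample size.** Section 11.1: "If 200 subjects are collected each in Phase I and in Phase II", "assuming a type I error of 0.05 and power of 0.80", the example being "a Phase I SND percentage of 10% at 6 months and a Phase II SND percentage of 20% at 6 months". Because "the study attrition rate may be 5% of the study population", the minimum becomes 210 per phase. No ICC or design effect appears.
- **Level of the intervention.** Section 4.3: investigators complete a workshop and are encouraged to use the toolkit to "create a practice specific process improvement intervention". Section 1.2 allows up to 10 sites.
- **Site in the design.** Section 4.4: "Centers will be used as their own control". Five subjects per site per phase is encouraged, and 42 is the maximum.
- **Expected heterogeneity.** Section 11.1: "the time to diagnosis is expected to vary by hospital".
- **Scope of the claim.** Section 1.1 expects the quality improvement methods to be useful more widely than in this study.

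**The concern.** Patients in one site and phase share whatever that practice did with the toolkit. If practices differ in how much they change, those patients are correlated and the pooled test's error term is too small for a conclusion about practices in general. A second problem is separate: the pooled test compares different mixes of sites if some recruit mainly in Phase I and others mainly in Phase II.

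The design makes each center its own control, but the overall test does not use that pairing. The study is a non-randomized before-after comparison, so its conclusion rests on this one contrast. A few responsive sites, or a changed mix, could yield a significant overall result.

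**Working it through.** **1. The plan's own figure.** Inputs from Section 11.1: 10% vs 20%, alpha 0.05, power 0.80, two-sided (the alternative is an inequality). Normal approximation with pooled rate 0.15:

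n = [1.96 × √(2 × 0.15 × 0.85) + 0.8416 × √(0.09 + 0.16)]² / 0.10² = (0.990 + 0.421)² / 0.01 ≈ 199 per phase.

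Power at 200 is 80.2%, so the stated 200 reproduces for independent patients. Attrition: 200 × 1.05 = 210.

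**2. The named test under independence.** I read the exact test as a two-sided Fisher test. Enumerating all tables at 200 per phase gives 76.8% power and an actual error of 3.4% at a 10% rate. Power is 79.2% at 210 and 80.1% at 214. This shortfall has nothing to do with clustering.

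**3. Site-by-phase variation.** Assumptions: 10 sites, 210 per phase, 10% in both phases, beta-binomial counts. ICC here means correlation within a site and phase beyond any site effect common to both phases. The implied SD of a site's true change is √(2 × 0.09 × ICC). Equal sites have 21 per phase; unequal sites range from 5 to 42. For power at 10% vs 20%, a paired t test on 10 equal sites (9 df) serves as a cluster-valid benchmark, with standard error √[(0.09 + 0.16)/21 × (1 + 20 × ICC)/10].

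| Assumed site-by-phase ICC | 0 | 0.01 | 0.02 | 0.05 |
|---|---|---|---|---|
| SD of site change (points) | 0 | 4.2 | 6.0 | 9.5 |
| Pooled Fisher error, equal sites | 3.4% | 5.4% | 6.9% | 13.3% |
| Pooled Fisher error, unequal sites | 3.5% | 6.1% | 9.4% | 17–18% |
| Design effect, 1 + 20 × ICC | 1.0 | 1.2 | 1.4 | 2.0 |
| Standard error of the change | 0.0345 | 0.0378 | 0.0408 | 0.0488 |
| Noncentrality, 0.10 / SE | 2.90 | 2.65 | 2.45 | 2.05 |
| Power, cluster-valid test, equal sites | 73% | 66% | 60% | 46% |

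The power row is simulated; the noncentral t gives 73%, 66%, 59% and 45%. The benchmark's own error stays at about 4% to 5.6%.

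**4. Stable site differences, same mix.** If sites differ in level, none changes, and each contributes equally to both phases, the pooled test rejects 2.6% to 3.1% of the time. There is no inflation.

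**5. Shifted mix, no site changes.** Illustration: low-rate sites at 5%, high-rate sites at 15%, and the low-rate share falling from 60% to 40%. Expected rates are 0.6 × 5 + 0.4 × 15 = 9% in Phase I and 0.4 × 5 + 0.6 × 15 = 11% in Phase II. The pooled test rejects 7.2% of the time; a shift from 70% to 30% gives 21.1%. Reversing unequal site sizes between phases gives 7.6% to 12.9% at between-site ICC 0.02 to 0.05. A site-stratified test on the same data stays at 4.6% to 5.2%.

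**6. Within-site tests.** With 210 / 10 = 21 patients per phase at an average site, these tests are small. They show where a change occurred but do not alter the overall p-value.

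**The case against.** Much of the opposing case stands.

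- **Everything is assumed.** No ICC is given, and only the site-by-phase part matters. At 0.05 the site changes have an SD of 9.5 points, as large as the target effect, while averaging zero. That is the far end of the range. The plan's remark about hospitals concerns time to diagnosis, not the change between phases.
- **Fixed sites.** If these sites are the whole population of interest and the mix is stable, the pooled test is valid for no change at any site. But Section 1.1 aims beyond them, and that inference needs site variation in the error term.
- **Site is not ignored.** Within-site tests are planned, and the cap of 42 is 20% of 210, so a result driven by a few sites should be visible. Visibility does not correct the overall p-value.
- **The planned test loses little nominal power.** Its rejection rate for 10% vs 20% falls only from about 79% to 72% over ICC 0 to 0.05 at 210 per phase, though its error rises over the same range. The 73% benchmark at ICC 0 reflects the 9-df t test, not a defect in the plan.

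A reader might infer that the error rate and power hold only if all sites change identically. The documents and figures do not support that. It is not necessary for the error rate, since the exact test's conservatism absorbs variation up to about ICC 0.01 with equal sites. It is not sufficient either, since a shifted mix inflates the error with no change anywhere, and Fisher power is below 80% even with identical sites. A reader might also see a contradiction with the statement on centers as controls. That statement describes a design measure: the same centers serve both phases. It is not carried into the overall test, which is an omission.

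**Conclusion.** The point holds as a gap in the overall analysis and in the power statement. The primary p-value makes no allowance for site-by-phase variation or for a shift in site mix, and the design leaves room for both.

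With 10 equal sites, the false-positive rate exceeds 5% from a site-by-phase ICC of about 0.01 and reaches about 13% at 0.05; unequal sites take it to about 18%. A reversal of site sizes alone gives about 8% to 13%. These figures rest on an assumed 10% rate, 10 sites and assumed correlations. The first effect matters for inference beyond the participating sites; the second is confounding even within them. The 76.8% power of Fisher's test is a separate, smaller matter and follows from the plan's own inputs once the exact test is read as Fisher's.

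None of this shows that a significant result would be false. It shows that the planned test could not separate a general effect from uneven site changes or a changed mix. The change should be made but does not block the study.

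**What to change.** In Section 11.1:

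1. Take the primary overall p-value and confidence interval from a logistic GEE or mixed model with phase as the effect, site as the cluster and a small-sample correction, weighting patients rather than sites equally. A mixed model needs a random site-by-phase term as well as a site intercept; the intercept alone would leave variation in the change out of the error.
2. At minimum, use a site-stratified comparison of phases. It removes site-mix confounding at no material cost in power when each site's share is similar in both phases, but does not address site-by-phase variation.
3. Keep the pooled exact test as supportive.
4. Do not make an unweighted site-paired t test primary when site sizes are unequal. With sites between 5 and 42 its power is only about 49% even at ICC 0.
5. Restate power: about 77% for the exact test at 200 per phase under independence, and roughly 73%, 66%, 60% and 46% for a cluster-valid test with 10 equal sites of 21 per phase at assumed ICC 0, 0.01, 0.02 and 0.05.

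The cost is plan wording, a little more analysis and a less favourable power statement. Site is already recorded, so no new patients or data are needed.
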